Additionally, our study population exhibits a low incidence of NSCLC patients, approximately 3-4%. Consequently, the current study is descriptive in nature.

Study Population

Patients in 20 Spanish hospitals (clinics, or and primary care centers) must have a confirmed diagnosis of locally advanced and/or metastatic NSCLC with an ALK rearrangement identified by an approved diagnostic test, be older or equal than 18 years and have initiated first-line therapy with lorlatinib at least 7 days and up to 28 days prior to enrolment in the study according to routine clinical practice. They must also sign an informed consent and have a minimum of predetermined data recorded in their medical records. Socio demographic data about the patient's gender, age, height, weight at the treatment initiation will be collected. Additional socio demographic data will be collected: race, along with details regarding their smoking habits, as well as exposure to asbestos and previous personal and family history of cancer, particularly in first-degree relatives. Patients included in clinical trials are also excluded.

Study variables

The following variables will be collected: AE, serious adverse events (SAE), and scenarios involving: exposure during breast feeding, medication error, overdose, misuse, extravasation, lack of efficacy; exposure during pregnancy (EDP), occupational/environmental exposure and treatment-associated mortality as well as time to onset and duration of AEs. Likewise, effectiveness variables as rwPFS rate at 12 and 18 months in the ITT population with and without brain; metastasis at baseline, rwDuration of Response (DoR); rwDuration of Treatment (DoT), rwTime to next therapy/treatment (TTNT)M; rwSystemic and intracranial Objective Response rate (ORR) using Response Evaluation Criteria in Solid Tumors (RECIST v1.1). criteria, rwTime to intracranial progression rate at 12 and 18 months with and without brain metastasis at baseline, rwCumulative incidence of brain metastases (BM) in ITT population at 12 and 18 months (with and without baseline BM), rwOverall survival (OS) rate at 12 and 18m.

Sociodemographic, clinical variables prior to start treatment/on treatment/after treatment with lorlatinib and quality of life data of patients under treatment will be collected.

Data sources

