8. RESEARCH QUESTION AND OBJECTIVES

Research question

 What is the spectrum of adverse events and mitigation strategies associated with lorlatinib as a first line treatment in an ALK+ NSCLC real-world Spanish population?

Primary Objective

• To describe all the spectrum of the adverse events (AEs) of Lorlatinib (CTCAE v6.0) and its mitigation strategies, with special interest in CNS AEs

Secondary Objectives

- To identify factors that are predictive of AEs, with special interest in CNS AEs
- To evaluate the effectiveness of 1L lorlatinib in real-world practice
 - 1. rwPFS rate at 12 and 18 months in the ITT population with and without brain metastasis at baseline.
 - 2. rwDuration of Response (DoR)

- 3. rwDuration of Treatment (DoT)
- 4. rwTime to next therapy/treatment (TTNT)
- 5. rwSystemic and intracranial Objective Response rate (ORR) using Response Evaluation Criteria in Solid Tumors (RECIST v1.1.) criteria
- 6. rwTime to intracranial progression rate at 12 and 18 months with and without brain metastasis at baseline
- 7. rwCumulative incidence of brain metastases (BM) in ITT population at 12 and 18 months (with and without baseline BM)
- 8. rwOverall survival (OS) rate at 12 and 18m
- To evaluate the impact of lorlatinib on patients' quality of life
- To describe ALK testing methods used

Exploratory Objectives (up to 30 patients)

• To identify neuroimaging markers (MRI) that are predictive of the occurrence of CNS AEs

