2. rwDuration of Response (DoR)	2. To determine real world duration of response (DOR), as the time from the first occurrence of a documented objective response to disease progression or death from any cause, whichever occurs first, as determined by the investigator according to RECIST v1.1. criteria (or Time from first documentation of CR or PR (whichever occurs first) after index until death or PD)			
3. rwDuration of Treatment (DoT)	3. To determine duration of treatment (DoT) as the time from lorlatinib's first dose to last dose for any cause. (Time to treatment discontinuation or Time from first dose to last dose of a treatment)			

4.	rwTime to next therapy/treatment (TTNT)	4.	To determine Time to next therapy/treatment (TTNT) as the Time from end of lorlatinib treatment to institution of next therapy	
5.	rwSystemic and intracranial Objective Response rate (ORR) using RECIST v1.1. criteria.	5.	To determine the systemic and real-world intracranial objective response rate (ORR) as determined by the investigator using RECIST v1.1. criteria	
6.	rwTime to intracranial progression rate at 12 and 18 months with and without brain metastasis at baseline	6.	Real world Time to intracranial progression rate at 12 and 18 months with and without brain metastasis at baseline	
7.	rwCumulative incidence of brain metastases (BM) in ITT population at 12 and 18 months (with and without baseline BM)	7.	Real world Cumulative incidence of brain metastases (BM) in ITT population at 12 and 18 months (with and without baseline BM)	
8.	rwOverall survival (OS) rate at 12 and 18m	8.	To determine the real-world overall survival (OS) rate at 12 and 18 months. OS is defined as the time from enrollment to death from any cause	
To evaluate the impact of lorlatinib on patients' quality of life.		of Pl Lo ar	hange from baseline in health-related quality f life (HRQoL), using the EORTC C30, RO_CTCAE (for CNS AEs) and submodules C13 at baseline, C1D15, C2D1, C3D1, C6D1 and every 3 months until the 1st year and then very 6 months	
To describe ALK testing methods used		Describe the different methods used to testing ALK mutations		
Exploratory Objectives (up to 30 patients)			Corresponding Endpoints	
To identify neuroimaging markers (MRI) that are predictive of the occurrence of CNS AEs		Fazekas scale, morphometric and radiomic analysis of baseline magnetic resonance images (MRIs) to identify imaging markers associated with the development of CNS AEs		

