- 1. **Baseline visit:** the day on which the patient fulfils the inclusion and exclusion criterion, including signature of the Informed Consent (i.e. the day on which the prospective observation starts) (within cycle 1 if lorlatinib)
- 2. Follow-up visit 1: will be scheduled at month 3 (third cycle of Iorlatinib)
- 3. Follow-up visit 2: will be scheduled at month 6 (sixth cycle of Iorlatinib)
- 4. Follow-up visit 3: Follow-up visit at month 12 (twelfth cycle of lorlatinib)
- 5. Final Visit: end of follow-up (end of data collection expected November 2027)

Data collection overview

Study Visits and Assessments	Baseline			FU3 C12D1	Final Visit
Informed consent	X				
SOCIO DEMOGRAPHIC DATA					
Medical history	X				
Physical examination including Height and weight	X	X	X	X	X

Study Visits and Assessments	Baseline	FU1	FU2	FU3	Final
		C3D1	C6D1	C12D1	Visit
Previous personal and family history of cancer	X				
CLINICAL DATA					
ECOG	X	X	X	X	X
Laboratory: Hematology and Blood chemistry (dyslipemia profile included). According to routine clinical practice	X	X	X	X	X
Comorbidities since Index Date: Charlson Index	X	X	X	X	X
Concomitant treatment(s) including previous history of Thromboembolic Disease	X	Х	X	X	X
Information of baseline tumor diagnosis: date, staging, (TNM),biopsy, PD-L1 expression, other mutations, etc	X				
Information regarding advanced disease: date, staging, metastatic location, CNS metastasis, previous systemic chemotherapy, radiotherapy, etc	X				
Previous systemic chemotherapy (Yes/No)	X				
Assessments CT scan	X				
Assessments brain MRI	X				
LORLATINIB TREATMENT					
Start, Stop and Discontinuation date	X	X	X	X	X
Dose by cycle	X	X	X	X	X
Reason for discontinuation or for dose reduction	X	X	X	X	X
Evaluation of Treatment Response: method (CT scan, MRI, others) and response	х	Х	X	X	X
AFTER LORLATINIB TREATMENT					

Study Visits and Assessments		FU1	FU2	FU3	Final
		C3D1	C6D1	C12D1	Visit
Post-progression treatment: type and palliative care					X
Date of death or last follow-up or last contact					X
QUALITY OF LIVE					
EORTC QLQ C30, LC13	X	X	X	X	X
SAFETY					
PRO-CTCAE	X	X	X	X	X
Adverse Events	X	X	X	X	X

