Height at tumor progression	patient's characteristics	Investigators Patient clinical record/Electronic Health record (EHR)	• Meters
Weight at tumor progression	patient's	Investigators Patient clinical record/Electronic Health record (EHR)	• kg
Post-progression treatment	patient s	Investigators Patient clinical record/Electronic Health record (EHR)	• Yes/No
Post progression treatment Type	patient's characteristics	Investigators Patient clinical record/Electronic	Chemotherapy, TKI (specify type), Immunotherapy,

Variable	Role	Data source(s)	Operational definition
		Health record (EHR)	Radiotherapy, Palliative Care.
Post progression treatments	On-treatment patient's characteristics		Describe subsequent treatment
Clinical data after lorlatinib completion			
Alive: Yes/No	After- treatment data	Investigators Patient clinical record/Electronic Health record (EHR)	• Yes/No
Date of death or last follow-up	After- treatment data	Investigators Patient clinical record/Electronic Health record (EHR)	Date format

Variable	Role	Data source(s)	Operational definition
Participant's perspective			
EORTC QLQ-C30	Outcome measure	Baseline, C3D1, C6D1, C12D1, Final visit	ePRO (through mobile device) questionnaire containing 30 questions and assesses the quality of life of oncological participants multidimensionally over 10 subscales.
EORTC QLQ-LC13	Outcome measure	Baseline, C3D1, C6D1, C12D1, Final visit	ePRO (through mobile device) questionnaire for lung participants. The QLQ-LC13 incorporates one multi-item scale to assess lung cancerassociated symptoms (i.e.coughing, haemoptysis, dyspnoea and pain) and side- effects from conventional chemo- and radiotherapy.
PRO-CTCAE (only for CNS AEs)	Outcome measure	Baseline, C3D1, C6D1, C12D1, Final visit	ePRO (through mobile device) questionnaire. When referring to CNS (Central Nervous System) adverse events, the PRO-CTCAE helps in assessing symptoms such as headaches, dizziness, and cognitive changes, which are crucial for understanding the impact of cancer treatments on the nervous system.

Variable	Role	Data source(s)	Operational definition
Exploratory variables (30 patients expected)			
To identify neuroimaging markers (MRI) that are predictive of the occurrence of CNS AEs	Exploratory analysis	MRI	Fazekas scale, morphometric and radiomic analysis of baseline magnetic resonance images (MRIs) to identify imaging markers associated with the development of CNS AEs.

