Only variables obtained according to routine clinical practice that follow objectives can and should be documented in this study and follow objectives.

To describe the safety profile of lorlatinib in the patients under the study, the following variables will be collected:

- AE, serious adverse events (SAE), and treatment-associated mortality.
- Time to onset and duration of AEs

Adverse events included in the study database will be coded according to CTCAE v6.0.

To study the safety profile, all adverse events that have been identified since the start of treatment with lorlatinib and related to the drug will be collected in the CRF. (More detail in section 11).

Researchers are reminded of their obligation to notify adverse reactions that the Pharmacovigilance Center as they are aware of.

Quality of Life (QoL) Assessments

Scales will be completed by patients at each study visit:

- EORTC QLQ C30: is a cancer-specific quality of life questionnaire (QLQ-C30), which consists of five functional scales (physical, role, cognitive, emotional, and social); nine symptom scales (fatigue, pain, nausea and vomiting, dyspnea, loss of appetite, insomnia, constipation, diarrhea, and financial difficulties); and a global health status/quality of life (GHS/QoL). Based on 30 questions in total, the scores range from 0 to 100. This questionnaire was approved and psychometrically validated (as well as each of its translations).
- QLQ LC13: the EORTC QLQ-LC13 is a supplementary questionnaire specifically designed for lung cancer patients. It is used in conjunction with the EORTC QLQ-C30 to assess the quality of life in these patients. The QLQ-LC13 focuses on lung cancer-specific symptoms and treatment side effects, such as coughing, shortness of breath, pain, and side effects from chemotherapy¹⁰.

• PRO-CTCAE (for CNS AEs)¹¹: is a tool developed by the National Cancer Institute (NCI) to capture symptomatic adverse events directly from patients receiving cancer treatment. It includes a set of questions that patients can answer to report the severity, frequency, and interference of symptoms they experience. When referring to CNS (Central Nervous System) adverse events, the PRO-CTCAE helps in assessing symptoms such as headaches, dizziness, and cognitive changes, which are crucial for understanding the impact of cancer treatments on the nervous system.

Exploratory variables (30 patients expected)

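### The protocol contradicts itself on whether quality-of-life and PRO-CTCAE questionnaires continue after lorlatinib is stopped

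*Protocol*

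**What the plan says.** The objective in Section 8 carries no on-treatment limit: "To evaluate the impact of lorlatinib on patients' quality of life". The places that say who is assessed, and when, differ.

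- **Abstract, Study variables.** One sentence covers clinical variables before, during and after treatment, but for quality of life it says "quality of life data of patients under treatment will be collected".
- **Section 9.1, endpoint table.** After baseline the assessments are at "C1D15, C2D1, C3D1, C6D1 and every 3 months until the 1st year", then six-monthly.
- **Section 9.2, visit list.** Visits are set by month with the cycle in brackets, for example "Follow-up visit 3: Follow-up visit at month 12 (twelfth cycle of lorlatinib". The final visit is the end of follow-up, expected in November 2027. The data collection table heads the same follow-up visits by cycle day and ticks QLQ-C30, LC13 and PRO-CTCAE at all five visits.
- **Section 9.3, variables table.** All three instruments are timed "Baseline, C3D1, C6D1, C12D1, Final visit", with no months.
- **Section 9.3, text.** "Scales will be completed by patients at each study visit", with no condition on treatment.
- **Section 10.3.** Progression and unacceptable toxicity are listed under withdrawal criteria. Continued follow-up is stated only for patients who refuse treatment without withdrawing consent.

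No schedule contains a questionnaire at permanent discontinuation.

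**The concern.** The objective concerns the effect of the drug on patients' quality of life, with special interest elsewhere in CNS toxicity. Patients who stop because of toxicity or progression are the ones whose scores are most likely to have worsened. If questionnaires end with treatment, the later means describe only those who tolerate lorlatinib and benefit from it. The SAP may choose how to handle missing scores, but it cannot recover questionnaires that sites were never asked to obtain. Who is assessed, and when, is settled in the protocol, and here the protocol gives more than one answer. Two sites could both comply and still treat the same patient differently after discontinuation.

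**Working it through.** **No protocol figure to reproduce.** The protocol gives no numerical target for quality of life. Its only computed figure is the sample size of 116 (Section 9.5), for CNS adverse events at 55% against 42%. A one-sample test at an assumed two-sided 5% level gives 114 by the normal approximation and 116 by the arcsine method, so 116 is a sound denominator below.

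**Reading the passages against one patient.** Take a patient who stops lorlatinib permanently in cycle 4.

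| Source | Questionnaires due after stopping |
|---|---|
| Abstract | None: no longer under treatment |
| 9.3 variables table | No C6D1 or C12D1 exists for this patient; the final visit only |
| 9.2 visit list with 9.3 text | Months 6 and 12, and the final visit |
| 9.1 endpoint table | C6D1 does not exist; the three-monthly and six-monthly points can still be met |
| 10.3 | Not stated if the reason was toxicity or progression |

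Under the cycle reading, the wait for the final visit can be long. Recruitment runs from 1 June 2025 to 30 November 2026 and data collection ends on 30 November 2027. The final visit therefore falls about 12 months (last patient in) to 30 months (first patient in) after enrolment.

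Months and cycles do not coincide even on treatment. Day 1 of cycle k comes after k - 1 cycles. If a cycle is about one month (the length is not stated), C3D1, C6D1 and C12D1 fall near months 2, 5 and 11, whereas the visit list equates them with months 3, 6 and 12.

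**Size if questionnaires did stop with treatment.** Inputs from Section 7, for the pivotal trial:

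- 20% progressed in the first 12 months. This equals the share off treatment only if patients stop at progression.
- The lower quartile of treatment duration on lorlatinib was 13.9 months, so about 25% were off treatment by then, and no more than that at month 12.

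Patients affected: 116 × 0.20 = 23.2, about 23; 116 × 0.25 = 29. Remaining: about 93 and 87.

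Overstatement of the mean = share off treatment × (mean on treatment - mean off treatment). The gap in brackets is not in the protocol and is assumed.

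| Share off | Gap 0 | Gap 5 | Gap 10 |
|---|---|---|---|
| 0.20 | 0 | 0.20 × 5 = 1.0 | 0.20 × 10 = 2.0 |
| 0.25 | 0 | 0.25 × 5 = 1.25 | 0.25 × 10 = 2.5 |

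The range is 1.0-2.5 points for a gap of 5-10 points. The formula treats everyone off treatment as alive and able to answer. Deaths would lower the number whose scores any change could recover.

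**The case against.** The strongest reply is that the body of the protocol already provides for patients who have stopped. The visit list puts the month first and the cycle in brackets. The scales are due at every visit, the final visit is the end of follow-up rather than of treatment, and the post-index period in Section 9.2 runs to the end of the study period. The abstract's clause may simply describe the cohort, since everyone enrolled is taking lorlatinib. All of this stands as evidence for one reading. It does not remove the others: the same abstract sentence names the post-treatment period for clinical data but not for quality of life, the variables table gives cycle days alone, and Section 10.3 is silent on the patients who matter most.

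A reader might infer more: that patients who stop certainly leave the series, that their next contact is the final visit, and that the result is biased by a definite amount. The documents do not support this. The month-based visits and the three-monthly and six-monthly points in Section 9.1 contradict the first two steps. The third needs a score gap that the protocol does not supply, and Section 7 reports that CNS adverse events had no negative effect on patient-reported quality of life in the pivotal trial. Nor can the 62% with temporary interruptions in that trial be read as visit drift in the first year: it accrued over a median of 57.0 months of treatment, and nothing says that interruptions move visits set by month.

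It is also fair to say that an extra questionnaire at discontinuation is a design preference, and that the analysis population and missing-data methods belong to the SAP. Neither is counted as an error here.

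**Conclusion.** The contradiction is real and should be resolved: the protocol does not settle whether, or on what schedule, questionnaires continue after lorlatinib is stopped. The bias is a risk under one permitted reading, not an established result. Its likely direction is favourable to lorlatinib, because toxicity and progression drive stopping. Its size is unknown. The 1.0-2.5 points rest on 20-25% being off treatment around month 12 (pivotal-trial figures, with stopping at progression for the lower one), an assumed gap of 5-10 points, and no questionnaires at all after stopping. Section 10.3 allows treatment beyond progression, so the share could be smaller, and with no gap the bias is zero. The endpoint is secondary and descriptive, which limits the consequences but not the need for a single instruction to sites.

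**What to change.** - **Abstract:** remove the on-treatment limit on quality-of-life data.
- **Sections 9.1, 9.2 and 9.3:** replace the differing timings with one schedule for QLQ-C30, LC13 and PRO-CTCAE, in months since the first lorlatinib dose. State that questionnaires are completed whether or not lorlatinib continues, unless consent is withdrawn.
- **Section 10.3:** state that stopping treatment, for any reason, does not in itself end questionnaire follow-up.
- **Optional:** add one electronic questionnaire at permanent discontinuation, to record quality of life when treatment ends.

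The cost is wording changes and a slight extra questionnaire burden for patients who stop. The questionnaires are already collected electronically for the study, so clinical management is unaffected. The main analysis population and the handling of missing scores can stay with the SAP.

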The investigators will collect the data of the patients included in an electronic data collection form (e-CRF) designed specifically for this study and developed by the CRO in charge at the beginning of the study. The data will be stored in an access database protected by password and only accessible to authorized personnel. Descriptive and survival analyses will be performed to evaluate the study objectives, using the Kaplan-Meier method and the Cox model. The AEs will be summarized by presenting the frequency distribution and percentage of these in the total number of patients and will be coded according to the CTCAE v6.0.

Imaging data^{9,10}

Brain MRI will be collected at baseline and in case of CNS toxicity. Images will be anonymized and centrally analyzed (See Section 9.3.7) to assess Fazekas scale, morphometric and radiomic features that will be correlated with CNS toxicity.

Baseline CT scan will be collected to determine the body composition. Images will be anonymized and centrally analyzed to assess radiomic features that will be correlated with CNS toxicity. Baseline body CT scan and brain MRI and first tumor assessment will be collected to determine body composition and to compare radiomic characteristics in patients who developed CNS AEs with those who did not.

Study size

In the CROWN trial, the incidence of CNS AEs was 42% and we assumed that the incidence could be higher in the real clinical practice, but it is probably under detected or recorded as most cases are grade 1. We estimated that we need 116 patients treated with lorlatinib in first-line therapy for ALK+ non-small cell lung cancer with an 80% power to detect an incidence of 55% any grade CNS AEs using a 2-sided test.

Data analysis

The safety assessment will be based primarily on the frequency and severity of AE. AEs will be summarized by presenting the number and percentage of these figures in the total number of patients. The absolute and variable frequencies of each AE with respect to the total number of reported AEs will also be presented. Descriptive analyses will be carried out to evaluate the objectives of the study.

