The study will capture results/data only from procedures that were actually performed as part of a participant's routine medical care, as determined by their treating physician.

Imaging analysis^{12,13}

Brain MRI will be collected at baseline and in case of CNS toxicity. Images will be anonymized and shared to assess Fazekas scale, morphometric and radiomic features that will be correlated with CNS toxicity.

The Fazekas scale will be calculated from the baseline MRI images of each patient. We will qualitatively evaluate the presence of White Matter hyperintensities on FLAIR images using a 4-point rating scale. Specifically, the assigned values for this rating scale were: 0 for no lesions, 1 for focal lesions, 2 for beginning confluence of lesions, and 3 for diffuse involvement of the entire regions with or without the involvement of U fibers.

The morphometric analysis will be completed by studying the volumetry of brain structures, including gray matter, white matter, and cerebrospinal fluid, which will also allow us to define the total intracranial volume. The morphometric analysis will be conducted using the SPM12 software (Welcome Department of Imaging Neuroscience Group) running on MATLAB (Mathworks). In patients with brain metastases at baseline, each of the lesions will be identified and delineated using T1-gadolinium and FLAIR (fluid-attenuated inversion recovery) utilizing the image analysis sequences, free software **MRIcron** (http://www.mccauslandcenter.sc.edu/mricron/mricron). The contrast-enhancing identified in the T1-gadolinium sequence will be defined as the tumor masks (ROI - region of interest). Similarly, the areas outlined in the FLAIR sequence will define the tumor edema compartment. In an initial analysis, the number of lesions, volumetric data (mm³) for each lesion, and the total sum of all lesions per patient will be calculated, as well as the tumor/edema ratio for each lesion and the sum of all lesions. We will perform an exploratory radiomics analysis, leveraging the masks (ROIs) previously defined in the morphometric analysis. After delineating the ROIs in the previous analysis, several variables related to texture and edge descriptors will be extracted. Weighted averages of each radiomics variable will be obtained for patients with more than one metastatic lesion. These averages will be weighted by the volume of the metastasis. All these parameters will be correlated with the CNS toxicity.

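### The imaging sub-study seeks predictors of CNS AEs, but its image time points conflict and allow scans taken after AE onset to enter as predictors

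*Protocol*

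**What the plan says.** Section 8 states the exploratory aim as a prediction question, "To identify neuroimaging markers (MRI) that are predictive of the occurrence of CNS AEs", under the label "Exploratory Objectives (up to 30 patients"). The endpoint in the section 9.1 table is the Fazekas scale with morphometric and "radiomic analysis of baseline magnetic resonance images (MRIs) to identify imaging markers associated with the development of CNS AEs". The exploratory row of the section 9.3 variables table repeats this. The data collection overview in section 9.2 ticks CT and brain MRI at baseline only.

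Three other places do not fit that picture.

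- The abstract, under imaging data, lists the first tumour assessment alongside baseline CT and brain MRI. These images are to be used for comparing patients with and without CNS AEs ("first tumor assessment will be collected to determine body composition and to compare radiomic characteristics in patients who developed CNS AEs").
- Section 9.3, imaging analysis, says "Brain MRI will be collected at baseline and in case of CNS toxicity", as does the abstract. After describing the volumetric and radiomic variables, section 9.3 concludes "All these parameters will be correlated with the CNS toxicity".
- Section 9.2 places the baseline visit at consent, within cycle 1. Inclusion criterion 2 in section 9.2.1 puts enrolment 7 to 28 days after lorlatinib was started.

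**The concern.** A predictor has to be measured before the event it predicts. A scan taken after a CNS AE has begun may show a consequence of the event, of treatment, or of a dose change made because of the event. If such a scan enters the comparison of patients with and without CNS AEs, a difference between the groups cannot be read as a marker of risk.

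The event-triggered MRI is the clearest case, because it exists only for patients who already have the toxicity. The first tumour assessment is less clear-cut, since for some patients it precedes onset and for others it follows. With at most 30 patients, a few misplaced images could be enough to suggest a marker. Which scans are requested and read centrally is fixed when images are collected, so the conflict is better settled in the protocol than left for the analyst to choose between passages.

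**Working it through.** The protocol gives no figure for this analysis beyond the ceiling of 30 patients, so there is no stated result to reproduce. The check is a comparison of the passages, followed by a simple count.

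**Step 1: which images does each place allow?**

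| Place | Images named |
|---|---|
| 9.1 endpoint table; 9.3 variables table | Baseline MRI |
| 9.2 data collection overview | CT and brain MRI at baseline only; response evaluation, by CT, MRI or other method, at every visit |
| 4 Abstract, imaging data | Baseline CT, baseline brain MRI, first tumour assessment, MRI at CNS toxicity |
| 9.3 imaging analysis | Baseline MRI, MRI at CNS toxicity, baseline CT; first tumour assessment not mentioned |

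Within the section 9.3 imaging text, the Fazekas score and the CT are tied to baseline, and lesion masks are described for patients who have brain metastases at baseline. The whole-brain volumes carry no time point, and the closing correlation sentence covers all parameters.

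**Step 2: time order of each image type relative to AE onset.**

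- *Baseline.* Section 11 starts AE reporting at the first dose. If the baseline image is tied to the baseline visit, it comes 7 to 28 days later, so an AE can start before it. If it means the staging scan done before treatment, the order is correct. The protocol does not say which is meant.
- *First tumour assessment.* It is listed separately from baseline, so I read it as on treatment. That is an inference. For any patient whose CNS AE started earlier, this image is post-onset.
- *Event-triggered MRI.* By construction it follows onset, and patients without CNS toxicity have none.

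**Step 3: how many patients could be affected?** Inputs are the ceiling of 30 (section 8) and the two incidences in section 9.5, 42% and 55%. These are whole-study figures, and applying them to the subset is an assumption.

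- Patients with a CNS AE: 30 × 0.42 = 12.6 and 30 × 0.55 = 16.5, so about 13 to 17.
- Event-triggered MRIs: at most that number of patients with one, against 0 among patients without a CNS AE.
- First-assessment images after onset: the protocol gives neither an onset distribution nor the timing of that assessment. Purely as an illustration, suppose 30% to 60% of onsets precede it and every affected patient's image is used. Then 12.6 × 0.30 = 3.8 and 16.5 × 0.60 = 9.9, or about 4 to 10 images.

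**Step 4: can the order be enforced with data already planned?** Yes. Section 9.3 collects time to onset of AEs, so each scan date can be set against the onset date.

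**The case against.** The strongest defence is that the abstract sentence is an outlier. The endpoint says baseline MRI in two tables, the visit schedule agrees, and the Fazekas score and CT are tied to baseline in section 9.3. The abstract sentence does not call the first-assessment images predictors, gives body composition as one of their purposes, and does not say that the first assessment includes a brain MRI. The analysis is also exploratory, in a study that describes itself as descriptive. This defence limits the severity and shows which reading was probably intended. It does not remove the conflict: the abstract still compares radiomic features by AE status at that time point, the event-triggered MRI is not excluded anywhere, and baseline is not defined as before the first dose.

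Stronger readings are tempting, but the document does not support them.

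- A reader might infer that the correlations will be unadjusted for age or head size. Section 9.3 does not say so. It derives total intracranial volume, the protocol collects age, and section 9.7 leaves the analyses to the SAP. Moreover, a marker associated with CNS AEs only through age would still be a real marginal association for a prediction question. Any inflation figure would rest on assumed correlations.
- A reader might fault the "tumor/edema ratio for each lesion and the sum of all lesions" as undefined for a lesion without oedema. That is a detail of feature definition.
- A reader might ask for a rule that takes the first 30 enrolled. The time-order problem does not call for one.

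**Conclusion.** The concern holds as a conflict over imaging time points. The objective and endpoint ask for baseline predictors, while other parts of the protocol admit first-assessment and event-triggered images and leave baseline loosely defined relative to the first dose. Images taken after AE onset can therefore enter a prediction analysis.

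The size cannot be fixed from the protocol. About 13 to 17 patients with a CNS AE are expected in a full subset of 30, and the figure of 4 to 10 post-onset first-assessment images is illustrative only. The finding does not depend on that figure. It rests on reading the first tumour assessment as on treatment, and on the absence of any statement that baseline scans precede the first dose.

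It would go too far to conclude that the sub-study cannot answer its question, because the baseline images named in the endpoint remain available. The severity is minor: the analysis is exploratory and no primary or secondary objective depends on it.

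**What to change.** Reconcile the abstract, the section 9.1 endpoint table, the section 9.2 schedule, and both the variables table and the imaging text of section 9.3, so that they name the same images for the same purpose. Specifically:

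1. Define the baseline image for the marker analysis as one acquired in routine care before the first lorlatinib dose, or at minimum before CNS AE onset.
2. Use first-assessment images in the marker analysis only for CNS AEs that start after that scan.
3. State that event-triggered and other post-onset images are descriptive and do not enter the predictor analysis.

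The cost is protocol wording and a comparison of scan and onset dates that are already to be recorded. The downside is a few fewer usable images in a subset of up to 30, because the study takes only scans done in routine care and some patients may have none that qualifies.
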